Appendix 6. A Weibull Proportional-Hazards Model for Event Time Data and Tipping Point Analysis

A Weibull Proportional-Hazards (WPH) Model

Let T_i be the time to event (observed or unobserved) and C_i the censoring time for subject i ($i = 1, 2, \dots, N$). We model the hazard function as,

$$h(t|x_i, \beta) = h_0(t)e^{\beta^T x_i}, \quad t > 0 \quad (1)$$

Here, β is a vector of unknown parameters corresponding to the vector of fixed effects x_i . There are three treatment groups, so the model term $\beta^T x_i$ when written out looks like,

$$\beta_1 x_{i1} + \beta_2 x_{i2}$$

Here, $x_{i1} = 1, x_{i2} = 0$ if subject i is randomized to PF-04965842 100 mg QD, $x_{i1} = 0, x_{i2} = 1$ if subject i is randomized to PF-04965842 200 mg QD and $x_{i1} = 0, x_{i2} = 0$ if subject i is randomized to placebo.

For further convenience, we also assume that $h_0(t)$ corresponds to the hazard function from the Weibull distribution with shape parameter $k > 0$ and scale parameter $\theta > 0$. So the survivor function $S(t; \beta^T x_i)$ amounts to,

$$\log(-\log S(t; \beta^T x_i)) = \beta^T x_i + k \log t - k \log \theta$$

In other words, this can be fit as a parametric regression model as,

$$\begin{aligned} \log t_i &= \log \theta - \frac{1}{k} \beta^T x_i + \frac{1}{k} \log(-\log S(t_i; \beta^T x_i)) \\ &= \beta_0 + \left(-\frac{\beta_1}{k}\right) x_{i1} + \left(-\frac{\beta_2}{k}\right) x_{i2} + \varepsilon_i \end{aligned}$$

with an intercept term as $\beta_0 = \log \theta$. Maximum likelihood estimates (MLE) for $\beta = (\beta_0, \beta_1, \beta_2)$ and k can be obtained using standard statistical software.

Tipping Point Analysis

Under censoring at random (CAR), $h(t|x_i, \beta)$ will be the same for all values of $t > 0$. If censoring is not at random (CNAR), then the post-censoring hazard $h^*(t|x_i, \beta), t > C_i$, will be different from $h^*(t|x_i, \beta), t \leq C_i$. We propose,

$$\begin{aligned} h^*(t|x_i, \beta) &= h_0(t) \exp\{\beta_1 x_{i1} + \beta_2 x_{i2}\}, \quad t \leq C_i \\ &= h_0(t) \exp\{\beta_1 (1 - \delta_1) x_{i1} + \beta_2 (1 - \delta_2) x_{i2}\}, \quad t > C_i \end{aligned}$$

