When $\delta_1 = \delta_2 = 0$, we are in the CAR situation. For any other values of (δ_1, δ_2) , we have CNAR. In particular, when $\delta_1 = \delta_2 = 1$, we have a jump to reference situation where we assume that post-censoring, the hazard rate is no different from that in the placebo (reference) arm. We note also that this formulation assumes CAR for the placebo arm.

The corresponding survivor function $S^*(t; \beta^T x_i)$ is,

$$\begin{aligned} \log(-\log S^*(t; \beta^T x_i)) &= \beta_1 x_{i1} + \beta_2 x_{i2} + k \log t - k \log \theta, & t \leq C_i \\ &= \beta_1(1 - \delta_1)x_{i1} + \beta_2(1 - \delta_2)x_{i2} + k \log t - k \log \theta, & t > C_i \end{aligned}$$

The WPH model, as described in equation (1) above, will be used as the imputation model. Estimation of the model parameters will be performed under the Bayesian framework using Markov Chain Monte Carlo (MCMC) methods. We assign a non-informative prior for each component of $\beta = (\beta_0, \beta_1, \beta_2)$ to be independent and identically distributed as $\sim N(0, 10^6)$ and assign a weakly informative prior for the Weibull shape parameter $k > 0$ as an Inverse-Gamma distribution with shape= 10^4 and scale= 10^4 .

Let $\{\beta^b = (\beta_0^b, \beta_1^b, \beta_2^b), k^b: b = 1, 2, \dots, B\}$ be a sample (seed = 1848654157) from the posterior distribution. A single imputation \widetilde{T}_i^b of the unobserved (or censored) T_i is based on the posterior predictive distribution of the event times estimated from the WPH model. For example, if subject i is censored at C_i , \widetilde{T}_i^b must be sampled from the conditional distribution of $\widetilde{T}_i^b | \widetilde{T}_i^b > C_i$. This can be easily done by equating the conditional survivor function $S^*(t | t > C_i, \beta^{bT} x_i)$ to a uniform random variable and solving for t . Under our Weibull model, we draw $u_i \sim U[0, 1]$ and solve,

$$S^*(t_i | t_i > C_i, \beta^{bT} x_i) = \frac{S^*(t_i; \beta^{bT} x_i)}{S^*(C_i; \beta^{bT} x_i)} = u_i,$$

which has a simple closed form solution as,

$$\begin{aligned} k^b (\log t_i - \beta_0^b) \\ = \exp(\beta_1^b \delta_1 x_{i1} + \beta_2^b \delta_2 x_{i2}) \log \left\{ -\exp(-\beta_1^b x_{i1} - \beta_2^b x_{i2}) \log u_i + \left(\frac{C_i}{e^{\beta_0^b}}\right)^{k^b} \right\} \end{aligned}$$

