Analysis of an imputed data set will produce an estimate as well as standard error of the hazard ratios using a Cox model as described in [Section 5.2.4](#). For given values of CNAR parameters (δ_1, δ_2) , this is repeated for B (typically, $B=500$) times to generate B complete imputed data sets and these B sets of estimates are combined using the Rubin's Method (Rubin, 1987). This can then be repeated for different values of MNAR parameters (δ_1, δ_2) to evaluate the impact of missing data. Note that $(\delta_1, \delta_2) = (0, 0)$ corresponds to an MAR analysis and $(\delta_1, \delta_2) = (1, 1)$ corresponds to an analysis commonly known as Jump-To-Reference (JTR).

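### The survivor function and imputation formula printed in SAP Appendix 6 do not follow from the post-censoring hazard it states, so the tipping-point analysis is wrong as written for any non-zero delta

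*SAP*

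**What the plan says.** SAP 5.3.3 and 6.1.1.2 plan a tipping-point analysis of time to flare in FAS-RA, with multiple imputation for subjects who discontinue without an event. In SAP Appendix 1 it is the only censoring-not-at-random row.

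Appendix 6 supplies the mathematics. "If censoring is not at random (CNAR), then the post-censoring hazard" differs from the hazard before C. Write β for the log hazard ratio of the subject's active arm against placebo, δ for that arm's sensitivity parameter, and θ for e^β0. The stated hazard is then h0(t)·exp(β) up to C and h0(t)·exp{β(1−δ)} after C. At δ = 1 the plan says that after censoring "the hazard rate is no different from that in the placebo (reference) arm".

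"The corresponding survivor function" is then given for t > C as log(−log S*) = β(1−δ) + k log t − k log θ. An imputed time "must be sampled from the conditional distribution of" T given T > C, found by setting S*(t)/S*(C) equal to a uniform draw u, "which has a simple closed form solution as": k(log t − β0) = exp(βδ) · log{−exp(−β) log u + (C/θ)^k}.

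**The concern.** The hazard, the survivor function and the solution should be three statements of one model. They agree at δ = 0 and disagree elsewhere. A programmer who codes the closed form and another who solves the printed S* would impute different times from the same data, and neither would be using the stated hazard. What is at stake is the only check on informative censoring for the primary endpoint: the δ at which the result tips depends on which line was coded, and the run labelled Jump-To-Reference would not be one.

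**Working it through.** **Inputs.** The hazard, S*, the T > C rule and the closed form come from SAP Appendix 6. The hazard ratio comes from the design ratio of medians, 1.5 (SAP 2.2, Sample Size Determination): at k = 1, HR = 1/1.5 = 0.667. The documents do not give θ, so I take the value at which the stated 94% power holds. Events needed are 4(1.960 + 1.555)²/(ln 1.5)² = 300.6 among 400. With exponential times over 40 weeks and no dropout, 200[(1 − e^−Λ) + (1 − e^−0.667Λ)] = 300.6 gives Λ = 1.719. That means 82% flare on placebo, 68% on active, and θ = 40/1.719 = 23.27 weeks. k = 1 and all dropout rates are assumptions.

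**1. Integrate the stated hazard.** For t > C:

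−log S*(t) = exp(β)(C/θ)^k + exp{β(1−δ)}[(t/θ)^k − (C/θ)^k].

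The printed version is exp{β(1−δ)}(t/θ)^k. The two agree only if β = 0 or δ = 0.

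**2. The jump.** At C = 20, δ = 1, the printed line for t ≤ C gives exp(−0.667 × 20/23.27) = 0.56, and the line for t > C gives exp(−20/23.27) = 0.42. The ratio 0.42/0.56 = 0.75 means that about a quarter of the uniform draws have no solution beyond C.

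**3. Solve for t.**
- Stated hazard: k(log t − β0) = log{−exp(−β(1−δ)) log u + (C/θ)^k}.
- Printed S*, with S*(C) on the t ≤ C line: k(log t − β0) = βδ + log{−exp(−β) log u + (C/θ)^k}.
- Printed closed form: the same logarithm, *multiplied* by exp(βδ).

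Substitution at k = 1.3, θ = 30, β = −0.8, δ = 0.6, C = 20, u = 0.40: the closed form gives t = 47.5, which returns 0.410 under the hazard and 0.348 under the printed S*. Neither is 0.40. The correct draw is 48.2.

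**4. Imputed times before C (β < 0, δ > 0).** With c = C/θ and k = 1:
- printed S*: 1 − exp{−e^β · c · (e^−βδ − 1)}, positive for every C;
- closed form: 1 − exp{−e^β(c^m − c)} with m = e^−βδ when c > 1, otherwise 0;
- stated hazard: always 0.

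θ = 23.27, HR 0.667, δ = 1:

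| Censored at | Stated hazard | Closed form | Printed S* |
|---|---|---|---|
| Week 10 (c = 0.430) | 0% | 0% | 1 − e^−0.143 = 13% |
| Week 30 (c = 1.289) | 0% | 1 − e^−0.116 = 11% | 1 − e^−0.430 = 35% |

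The size depends on k. With placebo median 16 weeks, HR 0.30, C = 28 and δ = 1, the closed-form share is 7%, 19% and 62% at k = 0.8, 1 and 1.5; the printed S* share is 53%, 57% and 68%.

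**5. Not Jump-To-Reference at (1,1).** With placebo median 16 weeks, HR 0.667 and k = 1, the true median time from censoring to imputed event is 16.0 weeks whatever C is. For C = 4 the closed form gives 22.3 and the printed S* 14.7; for C = 28 they give 11.7 and 6.7. The closed form errs in opposite directions at the two times.

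**6. Effect on the hazard ratio at δ = 1.** Simulation: 1,500 trials, 200 per arm, 40 weeks, HR 0.667, 82% placebo flare, k = 1, Cox fit, Rubin's rules. Imputed times were kept as events, since Appendix 6 states no cut at the end of the blinded period. In the order stated hazard / closed form / printed S*:
- 15% dropout: 0.694 / 0.699 / 0.709;
- 30% dropout: 0.720 / 0.731 / 0.749.

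If imputed times are instead cut at week 40, the closed-form difference in log HR at 15% dropout is −0.0023; uncut it is +0.0077.

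**7. Tipping δ, uncut (stated hazard against closed form).** At θ = 23.3, HR 0.667, 30% dropout: 2.7 against 4.5, so later. At θ = 11.5, HR 0.75, 30% dropout: about 3.5 against 2.5, so earlier. At θ = 23.3, HR 0.76, 30% dropout: about 0.8 against 0.6, also earlier.

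**The case against.** **It may be a misprint.** In the PDF-converted text, exp(βδ) stands outside the logarithm; its position should be checked on the page. Moving it inside makes the closed form solve the printed S* exactly, but that S* still contradicts the hazard, so a typographical correction is not enough.

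**The S* error might cancel.** If S*(C) were evaluated on the t > C line as well, the ratio would reduce to the correct draw. But the SAP assigns t = C to the other line, and its closed form, with exp(−β) in front of log u, matches that assignment.

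**The intent is clear.** This is fair. The hazard, the verbal meaning of (1,1), the T > C rule and the cited method all point to the right model, and a check that T exceeds C would expose imputations before censoring. The documents contain no program, so nothing shows that the printed lines were coded.

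**The size is small and the assumptions are mine.** This also stands at δ = 1, the only non-zero value that the SAP names. Larger differences in the simulations rest on assumed larger δ, heavier dropout or a stronger effect. The choice k = 1 rests partly on the plan's prior (it says it will "assign a weakly informative prior for the Weibull shape parameter"), whose exponents as converted nearly fix k at 1 and should also be checked on the page.

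**A tempting stronger reading** is that the closed form flatters the drug by always tipping later. Step 7 shows that it can tip later or earlier, so no fixed direction can be claimed.

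**Conclusion.** Appendix 6 is wrong as written for every non-zero δ when β is not zero. That rests on algebra alone for the survivor function; for the closed form it also depends on the printed position of one factor. At the design effect, with k = 1, uncut imputations and assumed dropout of 15% to 30%, the hazard ratio at δ = 1 moves by about +0.005 to +0.012 under the closed form and +0.015 to +0.03 under the printed S*. No form tipped at δ = 1 in the simulations at the design effect and the flare rate implied by 94% power.

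A reader might infer that the primary result is in doubt. The documents do not support that: the censoring-at-random analysis, the test hierarchy, the placebo imputations and the (0,0) run do not use the faulty lines. What is in doubt is the reported tipping δ and the Jump-To-Reference label, and only if the printed lines were coded.

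**What to change.** Replace two equations in Appendix 6. For t > C, with sums over the two arm indicators:

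−log S*(t) = exp(Σβx)(C/e^β0)^k + exp{Σβ(1−δ)x}[(t/e^β0)^k − (C/e^β0)^k]

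Impute:

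t = e^β0 · [(C/e^β0)^k − exp{−β1(1−δ1)x1 − β2(1−δ2)x2} · log u]^(1/k)

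At δ = 1 this is the placebo residual-time draw. Check the analysis program against both equations, and add a test that every imputed time exceeds C. The cost is two lines of the SAP and a program check; no new data and no change to the design are needed.

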Appendix 7. Schedule Of Activities

SCHEDULE OF ACTIVITIES FOR RUN-IN AND BLINDED TREATMENTS

The schedule of activities table provides an overview of the protocol visits and procedures. Refer to the STUDY PROCEDURES and ASSESSMENTS sections of the protocol for detailed information on each procedure and assessment required for compliance with the protocol.

The investigator may schedule visits (unplanned visits) in addition to those listed on the schedule of activities table, in order to conduct evaluations or assessments required to protect the well-being of the subject.

Visit Identifier	Day -28 ^a Screening	Day 1 Week 0 Baseline	Day 8 Week 1 Call	Day 15 Week 2	Day 29 Week 4	Day 43 Week 6 Call	Day 57 Week 8	Day 85 Week 12 Randomize Responders	Day 113 ^b Week 16	Day 197 ^b Week 28	Day 281 ^b Week 40	Day 365 ^b Week 52 EOT/ET	EOS, Follow-up Week 56/ 4 Weeks post ET
	Visit 1	Visit 2	Visit 3	Visit 4	Visit 5	Visit 6	Visit 7	Visit 8	Visit 9	Visit 10	Visit 11	Visit 12	Visit 13
Visit Window	None	None	±1 Day	±1 Day	±2 Days	±3 Days	±3 Days	±3 Days	±3 Days	±7 Days	±7 Days	±3 Days	±3 Days
Enrollment Procedure													
Informed consent ^c	X												
Register subject using IRT system	X												
Inclusion/Exclusion Criteria	X	X						X					
C-SSRS ^d	X	X					X	X	X	X	X	X	X
SBQ-R ^d	X												
PHQ-8 ^d	X												
Demographics, Medical History, Tobacco and Alcohol History, Atopic Dermatitis Disease History ^e	X												
Review Prior/Concomitant Medications & Treatments	X	X	X	X	X	X	X	X	X	X	X	X	X
Dispense e-Diary and instruct subjects on use	X												
Provide Patient Emergency Contact Card	X												

Visit Identifier	Day -28 ^a Screening	Day 1 Week 0 Baseline	Day 8 Week 1 Call	Day 15 Week 2	Day 29 Week 4	Day 43 Week 6 Call	Day 57 Week 8	Day 85 Week 12 Randomize Responders	Day 113 ^b Week 16	Day 197 ^b Week 28	Day 281 ^b Week 40	Day 365 ^b Week 52 EOT/ET	EOS, Follow-up Week 56/ 4 Weeks post ET
	Visit 1	Visit 2	Visit 3	Visit 4	Visit 5	Visit 6	Visit 7	Visit 8	Visit 9	Visit 10	Visit 11	Visit 12	Visit 13
Visit Window	None	None	±1 Day	±1 Day	±2 Days	±3 Days	±3 Days	±3 Days	±3 Days	±7 Days	±7 Days	±3 Days	±3 Days
Medical Procedures													
Complete Physical Exam ^f	X	X						X				X	
Targeted Physical Exam ^f				X	X		X		X	X	X		X
Vital Signs ^g	X	X		X	X		X	X	X	X	X	X	X
Weight/Height ^{dd}	X	X						X				X	
ECG (12-lead) ^{kk}	X	X		X	X		X	X	X	X	X	X	X
Laboratory Assessments^h													
Hematology ⁱ	X	X		X	X		X	X	X	X	X	X	X
Coagulation Panel ^j	X	X		X	X		X	X	X	X	X	X	X
Serum chemistry ^k	X	X		X	X		X	X	X	X	X	X	X
Urinalysis ^l	X	X		X	X		X	X	X	X	X	X	X
Lipid Panel ^m		X			X			X				X	X
Serum FSH (post-menopausal) or Pregnancy Test ⁿ	X												
Urine Pregnancy Test (conducted at study site) ^o		X		X	X		X	X	X	X	X	X	X
CCI													
HIV Testing ^q	X												
Hepatitis B Surface Antigen (HBsAg), Hepatitis B Surface Antibody (HBsAb), Hepatitis B Core Antibody (HBcAb), Hepatitis C Antibody (HCV Ab), Hepatitis C Viral RNA (HCV RNA) ^r	X												

Visit Identifier	Day -28 ^a Screening	Day 1 Week 0 Baseline	Day 8 Week 1 Call	Day 15 Week 2	Day 29 Week 4	Day 43 Week 6 Call	Day 57 Week 8	Day 85 Week 12 Randomize Responders	Day 113 ^b Week 16	Day 197 ^b Week 28	Day 281 ^b Week 40	Day 365 ^b Week 52 EOT/ET	EOS, Follow-up Week 56/ 4 Weeks post ET
	Visit 1	Visit 2	Visit 3	Visit 4	Visit 5	Visit 6	Visit 7	Visit 8	Visit 9	Visit 10	Visit 11	Visit 12	Visit 13
Visit Window	None	None	±1 Day	±1 Day	±2 Days	±3 Days	±3 Days	±3 Days	±3 Days	±7 Days	±7 Days	±3 Days	±3 Days
HBV DNA testing for China and Taiwan ^{jj}	X							X		X	X	X	
Varicella Zoster Virus (VZV IgG Ab) (adolescents only, if applicable) ^s	X												
Tuberculosis Test ^t	X											X ⁱⁱ	
Chest X-ray ^{hh}	X											X ⁱⁱ	
Pharmacokinetic													
Pharmacokinetic Blood Sampling (Post-dose) ^u								X					
Trial Treatment													
Randomization								X					
Drug Dispensing		X			X		X	X	X	X	X		
Investigational Product Accountability				X	X		X	X	X	X	X	X	
Investigational Treatment Administration ^v		X-----X											
Review eDiary to assess completion			X	X	X	X	X	X	X	X	X	X	
Assess eligibility for B7451015 ^w								X				X	
Clinical Assessments													
Fitzpatrick Skin Type Assessment		X											
Investigator’s Global Assessment (IGA)	X	X		X	X		X	X	X	X	X	X	X
SCORing Atopic Dermatitis (SCORAD)	X	X		X	X		X	X	X	X	X	X	X
Eczema Area and Severity Index (EASI)	X	X		X	X		X	X	X	X	X	X	X
Total Body Surface Area (BSA from EASI)	X	X		X	X		X	X	X	X	X	X	X

Visit Identifier	Day -28 ^a Screening	Day 1 Week 0 Baseline	Day 8 Week 1 Call	Day 15 Week 2	Day 29 Week 4	Day 43 Week 6 Call	Day 57 Week 8	Day 85 Week 12 Randomize Responders	Day 113 ^b Week 16	Day 197 ^b Week 28	Day 281 ^b Week 40	Day 365 ^b Week 52 EOT/ET	EOS, Follow-up Week 56/ 4 Weeks post ET
	Visit 1	Visit 2	Visit 3	Visit 4	Visit 5	Visit 6	Visit 7	Visit 8	Visit 9	Visit 10	Visit 11	Visit 12	Visit 13
Visit Window	None	None	±1 Day	±1 Day	±2 Days	±3 Days	±3 Days	±3 Days	±3 Days	±7 Days	±7 Days	±3 Days	±3 Days
Patient-reported Outcome													
Pruritus Numerical Rating Scale -eDiary (NRS) ^x	X-----X	X-----X		X	X		X	X	X	X	X	X	X
Patient Global Assessment (PtGA)		X		X	X		X	X	X	X	X	X	X
Dermatology Life Quality Index (DLQI or CDLQI) ^y		X		X	X		X	X	X	X	X	X	X
Patient-Oriented Eczema Measure (POEM)		X		X	X		X	X	X	X	X	X	X
Hospital Anxiety and Depression Scale (HADS)		X		X	X		X	X	X	X	X	X	X
Pruritus and Symptoms Assessment for Atopic Dermatitis - eDiary (PSAAD) ^z	X-----X	X-----X											
EQ-5D-5L (adults) or EQ-5D-Y (ages 12-17 years) ^{aa}		X		X	X		X	X	X	X	X	X	X
SF-36v2, Acute ^{bb} (adults)		X						X				X	X
FACIT-F (adults) or Peds-FACIT-F (ages 12-17 years) ^{cc}		X						X				X	X
Asthma Control Questionnaire (ACQ) for all subjects with a prior diagnosis of asthma		X						X				X	X
Safety													
Serious and non-serious adverse event monitoring	X →	→	→	→	→	→	→	→	→	→	→	→	→ X
Assess for presence of flare ^{cc}									X	X	X	X	
Contraception Check ^{ff}	X	X	X	X	X	X	X	X	X	X	X	X	X
Serum Sample for Baseline Viral Screen ^{gg}		X											

Abbreviations: ACQ = Asthma Control Questionnaire; BSA = body surface area; CDLQI = Children's Dermatology Life Quality Index; C-SSRS = Columbia Suicide Severity Rating Scale; DLQI = Dermatology Life Quality Index; EASI = Eczema Area and Severity Index; ECG = electrocardiogram; EOS=End of Study; EOT = End of Treatment; ET= early termination; EQ-5D-5L = EuroQol Quality of Life 5-Dimension 5-Level Scale; EQ-5D-Y = EuroQol Quality of Life 5-Dimension, Youth Scale; FACIT-F = Functional Assessment of Chronic Illness Therapy Fatigue Scale; FSH = follicle stimulating hormone; GGT = gamma-glutamyl transferase; HADS= Hospital Anxiety and Depression Scale; HBsAg = hepatitis B surface antigen; HBsAb = hepatitis B surface antibody; HBcAb = hepatitis B core antibody; HBV DNA = hepatitis B virus deoxyribonucleic acid; HCVAb = hepatitis C antibody; HCV RNA = Hepatitis C Viral RNA; Hep B = Hepatitis B; HIV = human immunodeficiency virus; HSV-1 = herpes simplex virus type 1; HSV2 = herpes simplex virus type 2; IGA = Investigator's Global Assessment; IgE = Immunoglobulin E; IRT = Interactive Response System; LDH = Lactate dehydrogenase; LLQ = lower limit of quantification; MCH = mean corpuscular hemoglobin; MCHC = mean corpuscular hemoglobin concentration; MCV = mean corpuscular volume; NK = Natural Killer; NRS = numerical rating scale; Peds-FACIT-F = Pediatric Functional Assessment of Chronic Illness Therapy Fatigue Scale; PHQ-8 = Patient Health Questionnaire 8 items; POEM= Patient-Oriented Eczema Measure; PSAAD=Pruritus and Symptoms Assessment for Atopic Dermatitis; PtGA = Patient Global Assessment; RBC = Red blood cell; RNA = Ribonucleic acid; SBQ-R = Suicide Behaviors Questionnaire-Revised; SCORAD = SCORing Atopic Dermatitis; SF-36v2 = Short Form-36 Health Survey Version 2;VZV = varicella zoster virus; VZV IgG Ab = varicella zoster virus immunoglobulin G antibody.

- a. Day relative to start of study treatment (Day 1).
- b. From Day 86 through Day 365, if the subject flares as defined by protocol, begin rescue treatment period. See Schedule of Activities for Rescue Treatment.
- c. Obtain written informed consent; for subjects aged under the legal age of majority (legal adulthood) in the subject's country, obtain written informed consent from legally acceptable representative/parent(s) or legal guardian, and informed assent from the patient (if age appropriate according to local regulations).
- d. Site staff is to administer the C-SSRS, SBQ-R and PHQ-8 to all subjects at screening and score immediately. Subjects who have recent or active suicidal ideation or behavior or clinically significant depression will be excluded from the study or discontinued from the study per Section 4.2, Section 7.5.1, Section 7.5.2 and Section 7.5.3. Subjects meeting exclusionary results on the C-SSRS, SBQ-R and PHQ-8 should be excluded from participation; it is recommended the subject's primary care physician (PCP) should be informed, and the subject referred to a mental health professional, either by the PCP or the investigator according to their usual practice. Post-screening, if there are "yes" answers on items 4, 5 or on any behavioral question of the Since Last Visit C-SSRS a risk assessment by a qualified mental health professional (MHP) should be done to determine whether it is safe for the subject to continue to participate in the trial.
- e. Atopic Dermatitis Disease History includes collection of details of AD: AD diagnosis and duration, the use of topical treatments, systemic treatments and other treatments for AD.
- f. Complete physical examinations must be performed by the investigator, sub investigator or a qualified health professional per local guidelines. Complete physical examinations consist of assessments of general appearance; skin; head, eyes, ears, nose and throat (HEENT); mouth, heart; lungs; breast (optional); abdomen; external genitalia (optional); extremities; neurologic function; and lymph nodes. Targeted physical examinations must be performed by the investigator, sub-investigator or a qualified health professional per local guidelines and should include skin, heart, lungs, and abdomen and examination of body systems where there are symptom complaints by the subject.
- g. Vital Signs include sitting blood pressure, pulse, respiratory rate, and temperature measured after at least 5 minutes of rest.
- h. Laboratory tests with abnormal results (per Section 6.1 and Section 7.6.2) may be repeated once during the screening period; the last value will be used to determine eligibility.

- i. Hematology includes: Hemoglobin, hematocrit, red blood cell count and indices (MCH, MCHC, MCV, RBC Morphology), white blood cells, neutrophils (%), lymphocytes (%), monocytes (%), eosinophils (%), basophils (%), platelets, reticulocyte count, lymphocyte subsets and markers (Total T cells [CD3+], CD4+ T cells [CD3+CD4+], CD8+ T cells [CD3+CD8+], NK cells [CD3- CD16+CD56+], B cells [CD3-CD19 +).
- j. Coagulation panel includes: Activated Partial Thromboplastin Time (APTT), Prothrombin Time/International Normalized Ratio (PT/INR).
- k. Serum chemistry includes: blood urea nitrogen (BUN), serum creatinine, creatine phosphokinase, glucose, Ca⁺⁺, Na⁺, K⁺, Cl⁻, total CO₂, aspartate aminotransferase (AST), alanine aminotransferase (ALT), gamma-glutamyl transferase (GGT), total, indirect and direct bilirubin, alkaline phosphatase, lactate dehydrogenase, uric acid, albumin and total protein.
- l. Urinalysis includes: pH, Glucose (qualitative), Protein (qualitative), Blood (qualitative), Ketones, Nitrites, Leukocyte esterase, Microscopy and/or culture (performed as appropriate).
- m. Lipid Panel includes: total cholesterol, low-density lipoprotein (LDL), high-density lipoprotein (HDL), and triglycerides. A minimum of 8-hour fasting is required for lipid profile evaluation at Day 1, Week 4, Week 12, Week 52 and EOS visits.
- n. Serum pregnancy testing at screening is required for women of childbearing potential including adolescents aged 12 years and older regardless of whether they have experienced menarche. Follicle stimulating hormone (FSH) test to be performed at Screening to confirm postmenopausal status in female subjects who have been amenorrheic for at least 12 consecutive months.
- o. Urine pregnancy test must be performed at every site visit prior to dosing with the investigational product for female subjects of childbearing potential including adolescents aged 12 years and older regardless of whether they have experienced menarche.
- █ [REDACTED]
- q. Subjects testing positive for HIV will be screen-failed.
- r. HBsAb reflex testing will be performed only if HBsAg negative but HBcAb positive. Subjects who are positive for HCVAb and HCV RNA will be screen-failed.
- s. VZV IgG antibody testing is required to confirm eligibility in adolescent subjects who have not received at least one dose of a varicella vaccine.
- t. A documented TB test performed within 12 weeks prior to Day 1 is acceptable. Subjects with a history of tuberculosis may not require TB testing as per the protocol exclusion criteria in Section 4.2. Perform TB test procedure using the QuantiFERON[®]-TB Gold In Tube Test (or Purified Protein Derivative). A negative PPD test can be substituted for the QuantiFERON[®]-TB Gold In-Tube test only if the central laboratory is unable to perform the QuantiFERON[®]-TB Gold In-Tube test or cannot determine the results to be positive or negative and the Pfizer Medical Monitor approves it on a case-by-case basis. In addition to protocol required TB testing, sites should follow their local standards for TB status determination, which may include chest X-ray. See Section 7.3.4.
- u. A PK blood sample will be collected at 2.0 hours (±30 min) postdose of open-label study drug (200 mg) at the Week 12 visit. For Early Termination (ET) visits, if the subject discontinues before Week 4, do not collect a PK sample. If the ET visit occurs at or after Week 4 and before Week 12, collect a PK sample only if the subject takes the investigational product at the site visit.

- v. Subjects should take the medication from study Days 1 to 365. Subjects will be encouraged to take the medication in the morning whenever possible; however, at study visit days, subjects are to be instructed to refrain from dosing at home and are to take the dose in the clinic. Instruct subjects regarding proper storage conditions for investigational product on Day 1.
- w. Subjects who are non responders but complete the 12 week run-in treatment and subjects who are responders at EOT will be assessed for eligibility for participation in long-term extension study B7451015 as noted in Section 6.3.5.
- x. Pruritus Numerical Rating Scale (NRS) will be assessed using an eDiary daily during the screening period and from Study Day 1 to 15. After Day 15, the Pruritus NRS will be completed only on study visit days in the eDiary. At the Screening visit, site staff will dispense the electronic tablet (ePRO device) and review instructions for completion of the subject eDiary for the NRS. At every visit, the study coordinator will review the eDiary for completeness and counsel the subject on how to complete the items in the daily eDiary, if needed.
- y. DLQI will be completed by adult subjects only. Adolescents 12-17 years of age will complete the CDLQI instead.
- z. Pruritus and Symptoms Assessment for Atopic Dermatitis (PSAAD) will be conducted (only in selected countries) to assess the severity and frequency of pruritus, symptoms and sleep collected daily in a subject e-diary during the screening period and from Day 1 through the End of Study visit (See Section 7.8.7). At the Screening visit, site staff will dispense the ePRO device and review instructions for completion of the subject eDiary for the PSAAD questionnaire. Subjects will be asked to record their assessment in their eDiary once a day before taking the investigational product. At every visit, the study coordinator will review the eDiary for completeness and counsel the subject on how to complete the items in the daily eDiary, if needed.
- aa. The EuroQol Quality of Life 5-Dimension 5-Level Scale (EQ-5D-5L) will be completed by adult subjects only. Adolescents 12-17 years of age will complete the EuroQol Quality of Life 5-Dimension, Youth Scale (EQ-5D-Y) in select countries.
- bb. SF-36v2 will be completed by adult subjects only. Adolescents 12-17 years of age will not complete this assessment.
- cc. FACIT-F will be completed by adult subjects only. Adolescents 12-17 years of age will complete the Peds-FACIT-F instead.
- dd. Height is not required at the baseline visit. Only adolescents (12 to <18 years old) require repeated height measurement at screening, Week 12, and EOT/ET visits. Adults require one height measurement at the screening visit.
- ee. Assess for the emergence of flare defined as a loss of at least 50% of the EASI response at Week 12 and an IGA of 2 or higher.
- ff. The contraception check is an opportunity to confirm that contraception, if assigned, is used consistently and correctly. It also facilitates continual reassessment of child-bearing potential in women. This allows for implementing necessary changes to contraception; for example, investigators may need to ensure alternative contraceptive methods if new concomitant disease contraindicates a selected method of contraception, or if a subject is demonstrably no longer of child-bearing status (as per protocol) then they will no longer require contraception. Continual reassessment of contraceptive needs is imperative.
- gg. A serum sample will be collected at baseline but analyzed only if the subject has suspected varicella or herpes zoster. In that event, the sample would be analyzed for HSV-1, HSV-2 and VZV.
- hh. Chest X-ray or other appropriate diagnostic image (ie, CT or MRI) may be performed up to 12 weeks prior to Study Day 1. Chest X-rays (posterior-anterior and lateral views) are required for adults and recommended for adolescents as per local guidelines and standard of care. Official reading must be located and available in the source documentation.
- ii. Following one year of total exposure to study drug since the last TB test, all subjects in regions which are above a low-risk for Tuberculosis (ie, >10/100,000 prevalence) will undergo tuberculosis (TB) testing. A chest X-ray will be performed to aid in TB status determination for all adults and recommended for adolescents according to local guidelines and standard of care in countries with a high incidence rate of TB.

- jj. In China and Taiwan only: Subjects who are HBsAg negative, HBcAb positive, and HBsAb positive at Screening will have reflex testing for Hepatitis B Virus (HBV) DNA. Subjects who have HBV DNA above the lower limit of quantification (LLQ) will be excluded. Subjects who are HBV DNA negative or below LLQ may enroll but will have HBV DNA testing repeated at Weeks 12, 28, 40, 52, and early termination from study during any treatment period. A single positive HBV DNA test result above the LLQ for a subject requires immediate and permanent discontinuation from treatment. Refer to Section 7.6.2.1.
- kk. A single 12-Lead ECG will be performed at screening and at all other planned on-site visits and interpreted by a central reader. Clinically significant or exclusionary ECG findings at the screening or baseline visits will require screen failure.

SCHEDULE OF ACTIVITIES FOR RESCUE TREATMENT - FLARE AT SCHEDULED OR UNSCHEDULED VISIT

Visit Identifier	Day 1 Week 0	Day 8 Week 1 Call	Day 15 Week 2	Day 29 Week 4	Day 43 Week 6 Call	Day 57 Week 8	Day 85 EOT/ET Week 12	EOS, Follow-up Week 16/ 4 Weeks post ET
	Rescue Visit 1	Rescue Visit 2	Rescue Visit 3	Rescue Visit 4	Rescue Visit 5	Rescue Visit 6	Rescue Visit 7	Rescue Visit 8
Visit Window	±3 Days	±1 Day	±1 Day	±2 Days	±3 Days	±3 Days	±3 Days	±3 Days
Enrollment Procedure								
Review Prior/Concomitant Medications & Treatments	X	X	X	X	X	X	X	X
Medical Procedures								
Targeted Physical Exam ^a	X		X	X		X		X
Complete Physical Exam ^a							X	
Vital Signs ^b	X		X	X		X	X	X
Weight/Height ^c	X						X	
ECG (12-lead)	X		X	X		X	X	X
Tuberculosis Test ^f							X	
Laboratory Assessments								
Hematology ^c	X		X	X		X	X	X
Coagulation Panel ^d	X		X	X		X	X	X
Serum chemistry ^e	X		X	X		X	X	X
Urinalysis ^f	X		X	X		X	X	X
Banked Biospecimen Sample Prep B1.5 ^g	X						X	
CCI								
Urine Pregnancy Test (conducted at study site) ⁱ	X		X	X		X	X	X
HBV DNA testing for China and Taiwan ^s							X	
Trial Treatment								
Drug Dispensing	X			X		X		
Investigational Product Accountability	X		X	X		X	X	
Investigational Treatment Administration ^j	X-----X							

Visit Identifier	Day 1 Week 0	Day 8 Week 1 Call	Day 15 Week 2	Day 29 Week 4	Day 43 Week 6 Call	Day 57 Week 8	Day 85 EOT/ET Week 12	EOS, Follow-up Week 16/ 4 Weeks post ET
	Rescue Visit 1	Rescue Visit 2	Rescue Visit 3	Rescue Visit 4	Rescue Visit 5	Rescue Visit 6	Rescue Visit 7	Rescue Visit 8
Visit Window	±3 Days	±1 Day	±1 Day	±2 Days	±3 Days	±3 Days	±3 Days	±3 Days
Review eDiary to assess completion	X	X	X	X	X	X	X	X
Assess eligibility for B7451015 ^k							X	
Clinical Assessments								
Investigator’s Global Assessment (IGA)	X		X	X		X	X	X
SCORing Atopic Dermatitis (SCORAD)	X		X	X		X	X	X
Eczema Area and Severity Index (EASI)	X		X	X		X	X	X
Total Body Surface Area (BSA from EASI)	X		X	X		X	X	X
Patient-reported Outcome								
Pruritus Numerical Rating Scale -eDiary (NRS) ^l	X-----X			X		X	X	X
Patient Global Assessment (PtGA)	X		X	X		X	X	X
Dermatology Life Quality Index (DLQI or CDLQI) ^m	X		X	X		X	X	X
Patient-Oriented Eczema Measure (POEM)	X		X	X		X	X	X
Hospital Anxiety and Depression Scale (HADS)	X		X	X		X	X	X
Pruritus and Symptoms Assessment for Atopic Dermatitis - eDiary (PSAAD)	X-----X							
EQ-5D-5L (adults) or EQ-5D-Y (ages 12-17 years) ⁿ	X		X	X		X	X	X
SF-36v2, Acute ^o (adults)	X						X	X
FACIT-F (adults) or Peds-FACIT-F ^p (ages 12-17 years only)	X						X	X

Visit Identifier	Day 1 Week 0	Day 8 Week 1 Call	Day 15 Week 2	Day 29 Week 4	Day 43 Week 6 Call	Day 57 Week 8	Day 85 EOT/ET Week 12	EOS, Follow-up Week 16/ 4 Weeks post ET
	Rescue Visit 1	Rescue Visit 2	Rescue Visit 3	Rescue Visit 4	Rescue Visit 5	Rescue Visit 6	Rescue Visit 7	Rescue Visit 8
Visit Window	±3 Days	±1 Day	±1 Day	±2 Days	±3 Days	±3 Days	±3 Days	±3 Days
Asthma Control Questionnaire (ACQ) for all subjects with a prior diagnosis of asthma	X						X	X
Safety								
C-SSRS [†]	X					X	X	X
Serious and non-serious adverse event monitoring	X→	→	→	→	→	→	→	→X
Contraception Check	X	X	X	X	X	X	X	X

- a. Complete physical examinations must be performed by the investigator, sub investigator or a qualified health professional per local guidelines. Complete physical examinations consist of assessments of general appearance; skin; head, eyes, ears, nose and throat (HEENT); mouth, heart; lungs; breast (optional); abdomen; external genitalia (optional); extremities; neurologic function; and lymph nodes. Targeted physical examinations must be performed by the investigator, sub-investigator or a qualified health professional per local guidelines and should include skin, heart, lungs, and abdomen and examination of body systems where there are symptom complaints by the subject.
 - b. Vital Signs include sitting blood pressure, pulse, respiratory rate, and temperature measured after at least 5 minutes of rest.
 - c. Hematology includes: Hemoglobin, hematocrit, red blood cells, white blood cells, neutrophils (% absolute), lymphocytes (% absolute), monocytes (% absolute), eosinophils (% absolute), basophils (% absolute), platelets, reticulocyte count, RBC Indices (MCH, MCHC, MCV, RBC Morphology), lymphocyte subsets and markers (Total T cells [CD3+], CD4+ T cells [CD3+CD4+], CD8+ T cells [CD3+CD8+], NK cells [CD3-CD16+CD56+], B cells [CD3-CD19+]).
 - d. Coagulation panel includes: Activated Partial Thromboplastin Time (APTT), Prothrombin Time/International Normalized Ratio (PT/INR).
 - e. Serum chemistry includes: blood urea nitrogen (BUN), serum creatinine, creatine phosphokinase, glucose, Ca⁺⁺, Na⁺, K⁺, Cl⁻, total CO₂, aspartate aminotransferase (AST), alanine aminotransferase (ALT), gamma-glutamyl transferase (GGT), total, indirect and direct bilirubin, alkaline phosphatase, lactate dehydrogenase, uric acid, albumin and total protein.
 - f. Urinalysis includes: pH, Glucose (qualitative), Protein (qualitative), Blood (qualitative), Ketones, Nitrites, Leukocyte esterase, Microscopy and/or culture (performed as appropriate).
-
- h. Lipid Panel includes: total cholesterol, low-density lipoprotein (LDL), high-density lipoprotein (HDL), and triglycerides. A minimum of 8-hour fasting is required for lipid profile evaluation at the following Rescue Visits: Day 1, Week 4, Week 12 and EOS visits.
 - i. Urine pregnancy test must be performed at every site visit prior to dosing with the investigational product for female subjects of childbearing potential including adolescents aged 12 years and older regardless of whether they have experienced menarche.

